7.0 Clinical Monitoring

The investigators will meet weekly (as close to that as permitted by travel and holidays) to monitor the study activities to ensure that the human participant protection, study procedures, administration, and data collection processes are of high quality and meet the appropriate, regulatory guidelines.

Standard monitoring procedures in place for tDCS therapy will be followed for this protocol. During tDCS therapy, operators are trained to monitor patients for any side effects. If a participant reports side effects, these are noted and dealt with according to severity. Importantly, tDCS does not directly induce neuronal firing and there has never been a reported case of tDCS induced seizure.

8.0 Statistical Analysis

8.1 Data Analysis

Specific Aim 1: Feasibility will be evaluated through participant retention, and will be calculated as the percentage of enrolled participants who complete the combined intervention. Acceptability will be evaluated by participant-rated satisfaction with the intervention, as rated on a 1-10 scale (where 1 is low satisfaction and 10 is high) collected at study completion.

Specific Aim 2: Mixed-factorial ANOVA will be used to examine between-group (Group A: active tDCS, versus Group B: sham tDCS) and within-group (time) effects on the main outcome measures: MCCB letter-number span score and MCCB spatial span score. Mean performance for each group at each time point will be plotted and examined.

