****NOTE: Aim 1 corresponds to NCT03338673 registered on clinicaltrials.gov. ****

Specific Aim 2: Collect pilot data on the efficacy of the combined intervention, comparing neurocognitive performance following active tDCS treatment to performance after cognitive training alone (sham tDCS). The proposed analyses will test the hypothesis that active tDCS plus computerized cognitive training will produce a synergistic effect, where performance following the combined treatment will be superior to performance following sham stimulation/cognitive training alone.

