****NOTE: Aim 2 is registered on clinicaltrials.gov as NCT05111548****

2.2 Study Outcome Measures

Aim 1: Determine the feasibility and acceptability of delivering a combined neuromodulation (tDCS) plus cognitive training intervention to outpatients with SMI.

Primary outcome: Participant retention, defined as the percentage of enrolled participants who complete the combined intervention.

Secondary outcome: Self-reported treatment satisfaction, as measured on a 1-10 scale at study completion.

Aim 2: Collect pilot data on the efficacy of the combined intervention, comparing neurocognitive performance following combined treatment to performance after cognitive training alone.

Primary outcome: change in working memory performance

Secondary outcome: change in non-working memory comparison measures

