4.4 Treatment Assignment Procedures

4.4.1 Randomization Procedures

Following baseline assessment, participants will be randomized to complete either the combined treatment (active tDCS plus cognitive training) or cognitive training alone (sham tDCS). Participants and clinical assessors will be blinded to condition; at the post-treatment assessment visit, participants and the assessor will guess group assignment to evaluate how well the blind was maintained.

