5.5 Assessments

Participants will complete assessments at three time points: baseline (pre-treatment), post-treatment, and follow-up.

Assessment schedule and administration time requirements.

	Baseline	Post-treatment	Follow-up	Administration time (mins)
Clinical measures				
MINI diagnostic interview	x			60
HAM-D, YMRS, PANSS	x	x	x	15-30
C-SSRS	x			5
Neuropsychological measures				
WRAT reading	x			5
MCCB (Trails A*; letter-number span; spatial span)	x	x	x	30
Trails B*	x	x	x	5
Functional measures				
SLOF	x	x	x	10
Total estimated time	≤ 2.5 hours	≤ 1.5 hours	≤ 1.5 hours	

*Trails A and B will be administered as non-working memory neurocognitive comparison measures

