6.2 Event Windows, Missed Assessments/Sessions and Protocol Deviation Reporting

For the post-treatment and follow-up assessments, a window of \pm 10 days will be permitted (not including weekends). Any safety-related assessments (HAM-D, YMRS, PANSS, C-SSRS) or primary outcome measure (MCCB working memory) which are missed or obtained outside the window will be reported to the IRB as a protocol deviation. However, for the other assessments, missing or late assessments will not be reported as protocol deviations unless they constitute > 10% of the total assessments. In order to accommodate inevitable scheduling conflicts, holidays, etc., participants will be allowed to complete the 10 tDCS sessions within 4 weeks. Participants who do not complete all 10 tDCS sessions or all 10 hours of cognitive training will be retained in the study and their outcome data will be compared to those participants who completed the full course of treatment. These allowances should affect neither the scientific integrity nor the safety monitoring provisions of the protocol.

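### Aim 2: the three-visit mixed-factorial ANOVA in section 8.1 yields no single estimate of the treatment effect on change; a baseline-adjusted active-minus-sham contrast with a confidence interval would, from scores already scheduled

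*Combined protocol and SAP*

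**What the plan says.** Section 8.1 gives the whole Aim 2 analysis in two sentences. The first is "Mixed-factorial ANOVA will be used to examine between-group (Group A: active tDCS, versus Group B: sham tDCS) and within-group (time) effects", applied to two main measures, "MCCB letter-number span score and MCCB spatial span score". The second is "Mean performance for each group at each time point will be plotted and examined".

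Other sections supply the context:
- **Visits (5.5):** "Participants will complete assessments at three time points: baseline (pre-treatment), post-treatment, and follow-up". Both span tests are scheduled at all three.
- **Baseline (4.4.1):** it precedes allocation: "Following baseline assessment, participants will be randomized to complete either the combined treatment".
- **Outcome (2.2):** "Primary outcome: change in working memory performance", with no score and no visit named.
- **Hypothesis (2.1, Specific Aim 2):** "performance following the combined treatment will be superior to performance following sham stimulation/cognitive training alone".
- **Missed visits (6.2):** a "primary outcome measure (MCCB working memory) which are missed or obtained outside the window will be reported to the IRB as a protocol deviation". The same section keeps people who do not finish treatment in the study, and 5.2.4 seeks the outcome assessments at early termination.

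No section names the interaction, a contrast, a main visit, a baseline adjustment, an effect estimate, a confidence interval, or a rule for reading the two scores together.

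**The concern.** The Aim 2 hypothesis has a direction and a place in time: active better than sham after treatment. The planned ANOVA offers two results that involve group, and neither has that form. Group-by-time is the natural reading, since the outcome is change and each group's mean is to be plotted at each visit. Over three visits, though, it is an omnibus test. The group main effect is one number, but it mixes a visit at which no treatment effect can exist with two at which it can.

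The protocol describes the study as a first step toward a larger randomised trial. What that trial needs is active minus sham at a stated visit, with its uncertainty. An F statistic and a plot do not supply it. If the visit and contrast are chosen after the plots are seen, across two scores, the choice can follow the data.

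Two further points bear on the method. Baseline is collected but not used as a covariate. In its classical form the ANOVA also drops anyone who misses one visit, which fits poorly with the effort in 5.2.4 and 6.2 to keep people and their outcome data.

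**Working it through.** **1. Inputs.** From the documents: 15 per arm (3.1, 3.4; 30 completers in the Protocol Summary), three visits, two scores. The documents give no alpha, power, effect size, SD or between-visit correlation, so there is no plan figure to reproduce. Assumed here: two-sided 0.05, SD 1, equal correlation rho between visits of 0.5/0.7/0.8, complete data, and effects d of 0.5 and 0.8 SD.

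**2. The interaction.** Numerator df = (3−1)(2−1) = 2; error df = 2 × (30−2) = 56. Noncentrality is lambda = (n/2) × S/(1−rho), where S is the sum of squared deviations of the three active-minus-sham differences from their mean.
- Effect sustained, (0, d, d): S = (4/9 + 1/9 + 1/9)d² = 0.667d².
- Effect gone by follow-up, (0, d, 0): S = (1/9 + 4/9 + 1/9)d² = 0.667d².

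The two profiles give the same lambda. At d = 0.8 and rho = 0.7 it is 7.5 × 0.667 × 0.64/0.3 = 10.67, and power is 82% for both. Reversing the sign of d changes nothing. A significant F therefore does not say whether the effect lasted or which arm did better.

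**3. The group main effect.** This is the mean of the three differences. For a true post-treatment effect of 0.80 SD:
- sustained: (0 + 0.80 + 0.80)/3 = 0.53 SD;
- gone by follow-up: (0 + 0.80 + 0)/3 = 0.27 SD.

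At rho = 0.7 its SE is sqrt((2/15)(1 + 2 × 0.7)/3) = 0.327, and power is 35% and 12%.

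**4. The adjusted contrast.** The post-treatment score is regressed on group and baseline, which stands here for the post-treatment contrast of the proposed model. SE = sqrt((2/15)(1−rho²)(1 + 1/26)); the last factor is the average cost of chance baseline imbalance. For unadjusted change, SE = sqrt((2/15) × 2(1−rho)). The 95% half-widths use t = 2.052 (27 df) and t = 2.048 (28 df).

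| rho | Adjusted | Unadjusted change | Narrower by |
|---|---|---|---|
| 0.5 | 2.052 × 0.322 = 0.66 | 2.048 × 0.365 = 0.75 | 12% |
| 0.7 | 2.052 × 0.266 = 0.55 | 2.048 × 0.283 = 0.58 | 6% |
| 0.8 | 2.052 × 0.223 = 0.46 | 2.048 × 0.231 = 0.47 | 3% |

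**5. Power, to see the cost.** Noncentral F(2,56) for the interaction and F(1,27) for the adjusted post-treatment contrast, at rho 0.5/0.7/0.8.

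| Effect at post-treatment, follow-up | Interaction | Adjusted post-treatment contrast |
|---|---|---|
| 0.5, 0.5 | 26/41/58% | 32/44/58% |
| 0.8, 0.8 | 59/82/95% | 67/83/93% |
| 0.8, 0.4 | 46/69/87% | 67/83/93% |
| 0.4, 0.8 | 46/69/87% | 22/31/41% |

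A simulation of 20,000 trials (d = 0.8 sustained, rho = 0.7) gave power of 35.2% for the main effect, 82.4% for the interaction and 82.6% for the adjusted contrast. The mean estimates were 0.53 SD for the main effect and 0.80 SD for the adjusted contrast.

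**6. Two scores.** If each is tested at 0.05 and the tests are independent, the chance of at least one false positive is 1 − 0.95² = 0.0975. Section 8.1 sets no rule for this.

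**The case against.** **The ANOVA does give an active-minus-sham number.** A reader might infer that it gives none. That goes too far: the group main effect is one. It is diluted by baseline (step 3), so what is missing is an estimate of the effect on change.

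**Section 8.1 does not exclude contrasts, effect sizes or intervals.** True; it is silent, and a pilot plan may be brief. But the visit and contrast are then left open until the data are seen, and a pilot has particular need of an estimate with its interval.

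**The fix could lose power.** This stands. A reader might infer that the adjusted contrast is the more powerful test. The figures do not support that in general: with a sustained effect and rho of 0.8 it is level with the interaction or 1–2 points below. If the effect is 0.4 SD at post-treatment and 0.8 SD at follow-up, it has 22/31/41% against 46/69/87%. The follow-up contrast covers this only in part, as it is secondary.

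**Post-treatment is the reviewer's choice.** Partly. The hypothesis in 2.1 speaks of performance after treatment, and 3.4 and 5.5 label a visit post-treatment, but no section makes it the main one. Section 1.0 also cites durability as a goal of cognitive remediation. A reader should not infer that the documents settle this.

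**Missing data are not ignored.** Sections 4.4.3 (investigator discretion over withdrawn participants' data), 5.2.4 and 6.2 all bear on them, and the sample size is set in completers. None says how an incomplete record enters the ANOVA. Dropping incomplete cases belongs to the classical form, which 8.1 does not specify.

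**Conclusion.** The point holds as a low-cost improvement. As written, the Aim 2 analysis gives a directionless 2-df test and a main effect that shrinks a true 0.80 SD effect to 0.53 or 0.27 SD. It gives no estimate of the treatment effect on change. A baseline-adjusted contrast gives one, with a 95% half-width of about 0.66/0.55/0.46 SD, which is 12/6/3% narrower than unadjusted change.

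The df count and the dilution follow from the design and the stated effect profiles. The half-widths and power figures rest on assumed SD, correlations and effects; only 15 per arm is documented. The case is for a defined estimate with an interval and makes no claim of reliably greater power. The planned ANOVA is not invalid as a test. These conclusions concern this document only; the registry record for Aim 2 was not available.

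**What to change.** Replace the Aim 2 text in section 8.1 with:

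> For each span score (letter-number span, spatial span), the main result is active minus sham at post-treatment, adjusted for the baseline score, with 95% CI, from a mixed model on post-treatment and follow-up scores (group, visit, group-by-visit, baseline, baseline-by-visit) using all available data as randomised, with small-sample degrees of freedom. The same contrast with 95% CI is reported at follow-up as secondary. Both scores are reported as pilot estimates; efficacy is not claimed from one score unless it was named primary in advance or a multiplicity adjustment is applied.

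The plot of group means stays. The investigators should confirm post-treatment as the main visit. If durability matters more to them, the two visits can change places before the data are seen.

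The cost is a few sentences and slightly more analysis work. No new data are needed, since both scores are already scheduled at every visit. The statistical price is the loss of power at post-treatment if the effect builds up only by follow-up.

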9.0 Source Documentation

Medical and research records will be maintained to ensure the protection of confidentiality of participants (see section 12). Only study staff will have access to these records.

10.0 Quality Control and Assurance:

The PI will review data collection and entry periodically to evaluate compliance with the protocol and for accuracy.

11.0 Ethics and Protection of Human Participants

11.1 Ethical Standard and IRB review

The investigator will ensure that this study is conducted in full conformity with the principles set forth in The Belmont Report: Ethical Principles and Guidelines for the Protection of Human Participants of Research, as drafted by the US National Commission for the Protection of Human Participants of Biomedical and Behavioral Research (April 18, 1979) and codified in 45 CFR Part 46 and/or the ICH E6; 62 Federal Regulations 25691 (1997) and the Declaration of Helsinki and Good Clinical Practice (GCP). All protocol amendments must be IRB approved prior to implementing, except when change is for patient safety.

11.2 Participant Confidentiality

11.2.1 Measures to protect patient privacy

Study staff will make every effort to limit identifiable information on potential participants during recruitment. Conversations in which a patient's name must be mentioned (e.g., to determine potential eligibility), will occur in private settings of the clinic. The minimum amount of information will be recorded, and staff will be alerted to the dangers of printing, faxing and emailing sensitive information. Phone conversations with potential research participants will occur behind closed doors, and staff will ask callers if they are in a location where sensitive information can be discussed without danger of revealing confidential information. Any information gathered on participants who prove ineligible will be destroyed as soon as possible (a list of patients who have declined or screened out will be maintained through the recruitment phase in order to avoid contacting these participants again).

11.2.2 Minimizing the potential for coercion of patients to participate

Because members of the research team are involved in clinical care and research, there is the potential that some patients of the study team may be recruited. It will be made clear to all potential participants that participation is entirely optional and not a part of regular treatment. The bulk of the recruitment process will occur with the study coordinator, who does not treat patients in any of the clinical venues where recruitment will occur. Overall, the research team is experienced in clinical research and very mindful of the conflict between the dual roles of clinician and researcher. They firmly believe that the safety and desires of the patient take precedence over any research protocol, and work hard to assure their patients that research participation is not required for treatment. In the case where a patient of a study team member is recruited, the consent process and signature on the informed consent document will be obtained by the study coordinator.

11.3 Potential Risks and Minimization of Risks

11.3.1 Risk Associated with Screening and Assessments:

1) Risk of boredom, fatigue, or discomfort (likely, not serious). It is possible that participants will become fatigued, frustrated, or uncomfortable answering sensitive questions about their mental health history.

To minimize risk: Participants may request a break from the procedures and/or may decline to answer any questions, though they will be counseled that this could affect their eligibility to continue their participation. If a participant becomes so upset that he/she cannot continue, he/she may be withdrawn without penalty.

2) Loss of confidentiality around sensitive information (rare, not serious).

To minimize risk: Paper records with identifying personal information (consent form, payment records) are stored separately from research records in locked file cabinets behind locked doors, to which only authorized research personnel have access. All data will include a subject identifier number and no personally-identifiable information. A single tracking file contains links to the research records and participant codes. Computer records with identifying information are kept on secure, password protected servers. Staff are trained to scrupulously protect the confidentiality of sensitive information, and take care to limit the printing of documents with identifying information and to avoid unnecessary discussion of participant names. Screening forms for participants who do not qualify for the study will be destroyed, except for anonymous information unlinkable to the participants (such as age, gender, and education).

11.3.2 Risk Associated with Computerized Cognitive Training:

1) Fatigue or boredom while completing training exercises (likely, not serious). The cognitive training exercises used in this study are completed while participants are seated in front of a computer monitor or tablet screen. There are no known risks for these procedures, as they are entirely non-invasive and painless. It is possible that participants will become fatigued or frustrated while completing the training.

To minimize risk: Participants may take a break from the procedure or postpone completion to another day or time.

11.3.3 Risks Associated with tDCS.

Active tDCS may have no benefit. The general consensus is that tDCS is extremely safe. In a meta-analysis of over 200 tDCS studies conducted from 1998 to 2010, 56% of studies mentioned adverse events¹². The events were generally minor, including itching, tingling, headache, burning sensation and discomfort limited to the scalp site where the tDCS electrodes were applied. To date, there have been no reports of seizures or other severe events induced by tDCS^{12,13}. Importantly this is the case in both healthy volunteers and in different populations of patients, including patients with disorders where there might be an increased risk of seizures (e.g. Alzheimer's disease, recent stroke, epilepsy). For this study, an intensity not to exceed 2 mA will be used, for a duration of 20 minutes; little of this current actually reaches the brain since it must first pass through the scalp (skin, fat, etc), skull, and cerebrospinal fluid. Few, if any, side effects are reported with these parameters and those that are reported are mild in nature (e.g., tingling, itching, burning sensation; Nitsche & Paulus, 2011). Nevertheless, side effects of tDCS are possible. The most common side effects associated with tDCS based on the available scientific data are:

1) Sensations under the electrode: these sensations usually stop shortly after tDCS begins but can sometimes continue throughout and for a brief period after tDCS.

- Mild tingling
- Light itching
- Slight burning sensation
- Discomfort

2) Reported effects that occur only DURING tDCS:

- Visual sensation during switching on and off the stimulation

3) Other effects that can occur both DURING and AFTER tDCS:

- Fatigue
- Skin redness
- Headache
- Changes in concentration, memory, or other cognitive abilities. This is partially what the proposed study will be testing.

Additionally, the following rare side effects have been described in previous studies that used tDCS:

- 1) Nausea
- 2) Nervousness
- 3) It is also possible that the electric current can cause a burn on the skin. This is unlikely because we are using a smaller dose than what is known to cause burns and because we use saline or gel to reduce electrical resistance that leads to burns.
- 4) A shock-like sensation at the initiation of tDCS was reported in one participant.
- 5) Changes in the activity of the prefrontal region (front of the head) have the potential to induce sudden changes in mood. Hypomania has been reported in a few patients receiving tDCS for bipolar disorder and depression.

To minimize risk: Clinically trained study staff will monitor participants closely for changes in mood or psychosis and/or any emergence of suicidal ideation throughout the duration of participation. In the event of significant symptomatic worsening (as detailed in 5.2.3 *Stopping Rules*), the PI will be promptly notified, and plans will be formulated for additional emergency evaluation at the psychiatric emergency room (University of Michigan Psychiatric Emergency Services), if appropriate. Similarly, if the evaluation of a

participant uncovers suicidal plans or intentions, the same procedures for emergency evaluation will be followed.

Importantly, the majority of the above side effects have also been reported in association with sham (fake) tDCS, with similar rates. The table below comes from a recent review of tDCS safety and shows the percentage of studies reporting these common sensations¹². These data suggest that other factors may cause these sensations, such as participant expectations or the pressure of head straps or caps.

Sensation	Real tDCS	Sham tDCS
Itching	39.3%	32.9%
Tingling	22.2%	18.3%
Headache	14.8%	16.2%
Burning	8.7%	10.0%
Discomfort	10.4%	13.4%

To minimize risk: The researchers will ensure that participants are fully informed of the risks during the informed consent process, and will adhere to best-practice standards for tDCS procedures.

Due to the investigational nature of the study, there may be risks, discomforts, or side effects that are not yet known.

For women of child-bearing potential: It is unknown if tDCS can pose a risk to fetuses or if it decreases milk production in women who are lactating.

To minimize risk: Participants are asked during their screening whether they are pregnant or are trying to become pregnant, or are currently lactating, and are not enrolled in the study if they are. Urine pregnancy screening can be made available to potential participants as requested. Sexually active women of child-bearing potential will be asked to use a reliable birth control method for the duration of this study.

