3.4 Schematic

Aim 1.

	Week 0	Weeks 1-4	End of Week 4	Weeks 5-8	Week 8
Group A (6 participants)	Baseline assessment	tDCS + BrainHQ	Mid-point assessment	BrainHQ	Post-treatment assessment
Group B (6 participants)		BrainHQ		tDCS + BrainHQ	

Aim 2.

	Week 0	Weeks 1-4	End of Week 4	Weeks 5-8	Week 8
Group A (15 participants)	Baseline assessment	Active tDCS + BrainHQ	Post-treatment assessment	No contact	Follow-up assessment
Group B (15 participants)		Sham tDCS + BrainHQ			

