4.2 Exclusion Criteria

(1) history of neurological illness or brain injury (e.g., stroke), (2) history of loss of consciousness > 20 minutes, (3) diagnosed intellectual disability, (4) current (i.e., past 30 days) substance use disorder, (5) current mania (YMRS \geq 10) or moderate depression (HAM-D \geq 17) or severe psychosis (PANSS positive symptom total \geq 35), (6) serious suicidal ideation/behavior (endorse questions 4 or 5 or suicide behaviors within the past 3 months, according to the C-SSRS), (7) pregnant or trying to become pregnant, or currently lactating, (8) presence of metal (except titanium) or electrical implants in the brain or skull (e.g., surgical clips, deep brain stimulator, cochlear implants, splinters/fragments, skull plate), (9) presence of implanted medical devices elsewhere in the body (e.g., cardiac pacemaker or medical pump).

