5.1.2 Initial Assessments

This session will continue with completion of a brief demographic questionnaire and clinical measures to confirm eligibility and characterize current symptoms. These include:

1. Mini-International Neuropsychiatric Interview (MINI), a short structured diagnostic interview for DSM-IV and ICD-10 psychiatric disorders
2. Hamilton Depression Rating Scale (HAM-D)
3. Young Mania Rating Scale (YMRS)
4. Positive and Negative Syndrome Scale (PANSS)
5. Columbia Suicide Severity Rating Scale (C-SSRS)

Note. To allow for maximal appropriate distancing owing to the ongoing COVID-19 pandemic, these interview-based clinical measures may be completed virtually while the participant is physically in the building and the clinician is in a remote location, via a secure and approved telehealth platform (Zoom for Health). Because the participant will be in the clinic with another study staff member (who will be administering the informed consent and the portion of the assessment that requires manipulation of materials), there are no anticipated changes to safety or risk-assessment protocols. Any safety concerns will be immediately communicated between the study clinician and research assistant, and appropriate action will be taken (see section 5.5.1).

Neuropsychological and functional measures will also be administered to characterize current neurocognitive functioning. These include:

1. Wide Range Achievement Test, reading subtest (WRAT-4)
2. MCCB: Trails A, letter-number span, spatial span
3. Trails B
4. Specific Levels of Functioning (SLOF) clinician-rated questionnaire

This screening and initial assessment visit is expected to last up to 2.5 hours.

5.2 tDCS Treatment visits

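### In Aim 1, the only required pregnancy check is a screening question, and no repeat is stated before Group B's first tDCS session, nominally about 4 weeks later

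*Combined protocol and SAP*

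**What the plan says.** Exclusion criterion 7 (section 4.2) covers anyone "pregnant or trying to become pregnant, or currently lactating". Section 11.3.3 gives the reason: "It is unknown if tDCS can pose a risk to fetuses or if it decreases milk production in women who are lactating". The same section sets out three measures:

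- A question at entry: "Participants are asked during their screening whether they are pregnant or are trying to become pregnant, or are currently lactating". Those who answer yes are not enrolled.
- An optional test: "Urine pregnancy screening can be made available to potential participants as requested".
- Contraception: sexually active women of child-bearing potential "will be asked to use a reliable birth control method for the duration of this study".

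In the Aim 1 schematic (section 3.4), Group A receives tDCS with BrainHQ in Weeks 1-4. Group B, also 6 participants, does BrainHQ alone in Weeks 1-4, has the "Mid-point assessment" at the end of Week 4, and receives tDCS with BrainHQ in Weeks 5-8. In Aim 2 both arms start their active or sham block in Week 1.

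Section 5.2.3 uses the mid-point assessment for safety: specified worsening on the YMRS, HAM-D or PANSS positive total leads to withdrawal. Pregnancy is not among the listed triggers.

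**The concern.** Criterion 7 works as an entry condition, but the exposure it guards against is stimulation. For Group A and both Aim 2 arms, the stimulation block directly follows entry. Group B is the only group with a full tDCS-free block in between.

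Following the plan as written, a Group B participant who became pregnant, or began trying to, during the BrainHQ-only block could start tDCS although the protocol would have refused her at entry. What is at stake is avoidable exposure to a risk that the protocol itself calls unknown. No efficacy estimate is involved.

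**Working it through.** The plan gives no figure on this point to reproduce. The check is a reading of the schedule plus simple arithmetic.

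**Inputs**
- Block timing and group sizes: section 3.4 (Group B, 6 participants, tDCS in Weeks 5-8; all other groups, Weeks 1-4).
- Timing of the question: section 11.3.3 says only that it is asked during screening. Assumption: it is asked at the Week 0 visit.
- Shortest Aim 1 course: 4 weeks (section 2.1 gives 4-8 weeks).
- Retention: completers of the combined intervention divided by those enrolled (sections 2.2 and 8.1).

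**1. Is a repeat stated anywhere?** None appears in the tDCS visit procedures (5.2.1), the stopping rules (5.2.3), the list of later assessments (5.4) or the assessment schedule (5.5). Section 6.1.3 has adverse-event questions at each treatment session but does not name pregnancy. The documents give no full list of mid-point contents, so the finding is that a repeat is not stated, not that it is not done.

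**2. Age of the recorded answer during tDCS**, as weeks elapsed since Week 0:
- Group B: about 4 weeks at the start of the block, about 8 at the end.
- Group A and both Aim 2 arms: about 0 at the start, about 4 at the end.
- Group B with a repeat at the end of Week 4: 4 − 4 = 0 at the start, 8 − 4 = 4 at the end.

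**3. If the question is asked earlier.** Section 4.5 describes a pre-screen, usually by telephone, and section 5.1.2 lists no pregnancy item for the first visit. Suppose the question is asked k weeks before Week 0. The answer is then 4 + k weeks old at Group B's first session and k weeks old for the others. Every gap lengthens, and the difference stays at (4 + k) − k = 4 weeks if k is the same across groups.

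**4. Shortest course.** If 4 weeks are split into two equal blocks (assumption), Group B runs from 2 to 4 weeks and Group A from 0 to 2.

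**5. How many are affected.** At most 6 of 12 Aim 1 participants, and only those who can become pregnant. The sex mix is not given. The documents supply no pregnancy rate, so no probability of exposure is calculated.

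**6. Retention cost of one person stopped**, with no other losses:
- 12 enrolled (section 3.1): 11/12 = 91.7%, down 8.3 points.
- 12 completers sought (Protocol Summary), so 13 enrolled: 12/13 = 92.3%, down 7.7 points.

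**The case against.** The strongest reply is that the interval is already covered. Those trying to conceive are excluded, contraception is requested for the study's duration, participants are told of the risks at consent, and they may withdraw at any time. The investigator may also withdraw anyone at unacceptable risk (section 4.4.2). The device is considered non-significant risk (section 5.2.2), and tDCS is rated as no more than minimal risk (section 11.4). By the end of their blocks, Group A and the Aim 2 arms are also being stimulated on an answer about 4 weeks old. A repeated question would miss an unrecognised early pregnancy.

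Much of this stands, and it is why the point is minor. It does not close the gap: a request for contraception and general adverse-event questions do not establish status before the first stimulation.

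A reader might infer more than the documents support:
- *That self-report is the only safeguard.* It is the only required check. The optional urine test and the contraception request are also stated.
- *That the gap is a documented 4 weeks.* It rests on the nominal schedule and an assumed Week 0 question.
- *That new lactation is an equal worry.* Anyone pregnant at entry is excluded, so lactation newly begun within 4 to 8 weeks is implausible.
- *That the protocol contradicts itself.* Criterion 7 is an entry criterion, and nothing in the text conflicts with it.

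**Conclusion.** The point holds as a minor safety refinement. In Aim 1 the required pregnancy check is a single self-report question at screening, and no repeat is stated before Group B's first tDCS session. On the nominal schedule the answer is then about 4 weeks old, or about 2 weeks on the shortest course split equally. Both figures assume that the question is asked at Week 0.

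The best argument for acting is consistency. The mid-point assessment already re-examines mania, depression and psychosis, which are also entry exclusions, and pregnancy has no stated equivalent. The reach is small, and Aim 2 is unaffected. A reader might take this as evidence that participants were exposed or harmed; the documents show neither.

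**What to change.** Add one line to section 5.2.3 or to the Aim 1 schedule. At the existing end-of-Week-4 mid-point visit, before Group B's first tDCS session, ask again about pregnancy and trying to become pregnant, with urine screening again available on request. Do not start tDCS in anyone who now meets criterion 7, and offer her the early termination assessments of section 5.2.4.

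The cost is a few minutes for at most 6 people at a visit already scheduled, plus a short wording amendment. The downside is that each person stopped counts as a non-completer, at the retention cost shown above. The repeat remains self-report unless a test is requested, and it does not cover changes later within the tDCS block.

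The documents do not say whether Aim 1 is complete. If it is, apply the same line to any later crossover or delayed-start use of the protocol.
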